12.3 Sample Size

If the mean Thoracic Kyphosis Correction of the RAIL system is 4.0 with a standard deviation of 8.4, then 173 subjects provides 80% power to detect a statistically significant difference between the mean correction and the OPC of 2.2 using a two-sided one-sample t-test at a significance level of 0.05. In order to account for approximately 15% attrition, based on clinical experience, 204 subjects will be enrolled.

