4.2 Treatment Group

Patients treated with the Ø5.5mm or Ø4.5mm MESA Rail Deformity System that had:

- Diagnosis of AIS requiring surgical treatment for selective thoracic/lumbar fusion with a minimum of five (5) instrumented vertebrae between T1-S1 as confirmed by patient history and radiographic studies. AIS cases must be classified as a Lenke type 1 or type 2 curve (lumbar modifiers and thoracic sagittal profiles will be noted but not restrictive). No cervical vertebrae are to be incorporated into the construct.
- An age at time of surgery of ≥ 11 years old and ≤ 21 years old.

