8.2.1 Pre-Operative Assessment

- Informed Consent/Assent
- Inclusion/Exclusion Criteria
- Demographics
- Pertinent History and Physical: Current Symptoms, Height, Weight and Tobacco Use
- Work/School Status

- Current Medication for Spine Problem
- Neurological Examination
- AP and Lateral X-rays
- Right and Left Lateral Bending X-rays (Pre-Operative Only)
- Back and Leg VAS and SRS-22r

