12.2 Study Hypothesis

The primary objective of this study is to evaluate the effectiveness of the MESA Rail Deformity System in terms of restoring and maintaining thoracic kyphosis in the treatment of patients with symptomatic AIS. The primary effectiveness endpoint is the rate of overall subject success (minimal loss of thoracic kyphosis) at 24 months. The primary hypothesis of this trial is that the clinical performance of the K2M MESA Rail implant is non-inferior to the clinical performance achieved and achieved with fusion utilizing a standard Ø5.5mm or Ø4.5mm CoCr rod.

A PubMed literature review was conducted to assemble relevant publications utilizing results from posterior instrumentation fusion surgeries in patients with AIS. Searches included all peer-reviewed journals published between January 2000 and March 2013. Sample sizes, patient populations, evaluated variables, results, and recorded complications were assessed for each selected article. Only data regarding thoracic kyphosis measurements of single-stage posterior fusion cases were incorporated into the thoracic kyphosis table used for statistical analysis. Articles were entirely excluded from the statistical analysis if results combined data from multi-stage cases or if data were extracted through meta-analysis.

The following table gives the preoperative thoracic kyphosis measurements as well as the thoracic kyphosis measurements collected at the last follow-up period from all relevant posterior fusion surgeries in patients with AIS:

| Thoracic Kyphosis | | | | | | | | | |
|----------------------------------|-----|-------|------|---------|------|------|------|---------------------|-------------|
| paper # | n | Preop | | Last FU | | Diff | | Mean difference x N | Std Dev x N |
| | | Mean | SD | Mean | SD | Mean | SD | | |
| 1 ¹ | 9 | 31.9 | 10.4 | 26.0 | 9.8 | 5.9 | 10.1 | 53.1 | 90.9 |
| 1 | 3 | 31.0 | 9.5 | 29.7 | 5.5 | 1.3 | 7.5 | 3.9 | 22.5 |
| 1 | 34 | 28.2 | 13.0 | 26.5 | 11.0 | 1.7 | 12.0 | 57.8 | 408.0 |
| 1 | 9 | 23.0 | 8.0 | 23.0 | 11.0 | 0.0 | 9.5 | 0.0 | 85.5 |
| 1 | 60 | 26.7 | 13.0 | 25.0 | 9.6 | 1.7 | 11.3 | 102.0 | 678.0 |
| 1 | 31 | 22.8 | 11.0 | 25.7 | 8.8 | -2.9 | 9.9 | -89.9 | 306.9 |
| 2 ² | 83 | 23.0 | 12.0 | 20.2 | 8.4 | 2.8 | 11.4 | 234.9 | 946.2 |
| 3 ³ | 111 | 29.0 | 14.0 | 23.0 | 10.8 | 6.0 | 12.2 | 666.0 | 1354.2 |
| 3 | 299 | 22.0 | 14.1 | 22.0 | 10.3 | 1.0 | 5.0 | 299.0 | 1495.0 |
| Weighted Mean Difference and SD: | | | | | | | | 2.1 | 8.4 |

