The study hypothesis is that the RAIL system is superior to other systems in Thoracic Kyphosis Correction. The hypotheses can be written:

$$\begin{aligned} H_0: \mu_R &< OPC - \delta \\ H_1: \mu_R &\geq OPC - \delta \end{aligned}$$

where μ_R is the mean Thoracic Kyphosis Correction of the RAIL system and OPC is the Objective Performance Criteria of 2.2 and $\delta = 2$ degrees.

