12.5 Analysis of Primary Endpoint

The primary effectiveness endpoint will be evaluated by a two-sided exact test of the MESA Rail implant success rate (mean thoracic correction) against the literature reported mean thoracic correction of 2.2 degrees.

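### The 2.2-degree literature benchmark is not shown to be CoCr and does not agree with its own table, sign or hypotheses, and the primary test has no check for pre-operative kyphosis

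*Combined protocol and SAP*

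**What the plan says.** **Comparator.** Sections 1 and 4.3 define the control as published results with 5.5 mm or 4.5 mm CoCr rods and pedicle screws.

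**Source of the benchmark.** Section 12.2 describes the literature table: "Only data regarding thoracic kyphosis measurements of single-stage posterior fusion cases were incorporated into the thoracic kyphosis table used for statistical analysis". It also excludes articles that mix in multi-stage cases or draw on meta-analysis. It gives no rule and no column for rod material.

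**Endpoint and hypothesis.** Section 12.2 first says "The primary effectiveness endpoint is the rate of overall subject success (minimal loss of thoracic kyphosis) at 24 months" and states a non-inferiority hypothesis. It then says "The study hypothesis is that the RAIL system is superior to other systems in Thoracic Kyphosis Correction", and writes H0 and H1 around OPC minus delta, with an OPC of 2.2 and a delta of 2 degrees.

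**Test.** Section 12.3 assumes a Rail mean of 4.0 and an SD of 8.4. It finds 173 subjects for 80% power to separate "the mean correction and the OPC of 2.2 using a two-sided one-sample t-test at a significance level of 0.05", and enrols 204 to allow for 15% attrition. Section 12.5 names an exact test of a success rate, yet sets it "against the literature reported mean thoracic correction of 2.2 degrees".

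**Baseline.** Section 4.2 leaves sagittal profile open at entry: "lumbar modifiers and thoracic sagittal profiles will be noted but not restrictive". Section 8.2.1 requires pre-operative "AP and Lateral X-rays", so pre-operative kyphosis will be available for everyone. Section 5.3.3 records percentage change, 12.7 summarises baseline variables and 12.8 examines baseline by site. None of these adjusts the primary test or compares the cohort with the literature patients.

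**The concern.** With no concurrent arm, the conclusion is only as good as the fixed number and the comparability of the patients behind it. Three things are at stake.

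- A conclusion about CoCr would rest on series not documented as CoCr.
- The threshold, the favourable direction and the type of claim cannot all be read consistently from Sections 12.2, 12.3 and 12.5. The same data could be called a success or a failure.
- If kyphosis change depends on the starting value, a Rail cohort that starts higher or lower than the literature patients could show a difference from 2.2 that has nothing to do with the device, or could hide a real one.

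**Working it through.** **1. The plan's own figure.** One-sample t-test, difference 4.0 − 2.2 = 1.8, SD 8.4, two-sided 0.05. Noncentral-t power is 79.8% at n = 172 and 80.03% at n = 173. Enrolment: 173/0.85 = 203.5, so 204. Both figures reproduce.

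**2. The OPC.** From the 12.2 table, the sum of n × mean difference is 1324.3 over N = 639, which gives 2.07. The printed products sum to 1326.8, which gives 2.08. Either rounds to the printed 2.1; neither gives 2.2. The largest row reads "3 | 299 | 22.0 | 14.1 | 22.0 | 10.3 | 1.0 | 5.0 | 299.0 | 1495.0": 22.0 at both times, but a difference of 1.0. With 0 in that row the mean is (1324.3 − 299)/639 = 1.60. If the true Rail mean equals the table mean, testing against 2.2 at n = 173 and SD 8.4 rejects in 5.5% of trials at 2.07 (gap 0.13) and 15.4% at 1.60 (gap 0.60).

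**3. The sign.** In the first row 31.9 − 26.0 = 5.9. The difference is pre-operative minus last follow-up, so positive means kyphosis was lost. Section 12.2 defines success as minimal loss. Section 12.3 sizes the trial on 4.0 against 2.2 as the favourable case.

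**4. The hypothesis.**

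| Place | Claim | Threshold |
|---|---|---|
| 12.2, first statement | non-inferior, endpoint a rate | none given |
| 12.2, formal hypotheses | superior in words, mean correction | 2.2 − 2 = 0.2 |
| 12.3 | mean differs, two-sided t-test | 2.2 |
| 12.5 | exact test of a rate | 2.2 degrees |

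**5. Does change depend on pre-operative kyphosis?** Within a row, the slope of (pre − follow-up) on pre is 1 − r × SDfu/SDpre. Because r cannot exceed 1, the slope is at least 1 − SDfu/SDpre. In table order the floors are 0.058, 0.421, 0.154, −0.375, 0.262, 0.200, 0.300, 0.229, 0.270. Eight of nine are positive. The n-weighted floor is 0.245, or 0.223 without the n = 299 row. The n-weighted between-row slope is 0.54 (95% CI 0.10 to 0.97), but it is fragile: 0.23 (p = 0.34) without the n = 111 row. The table suggests dependence; it does not establish it.

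**6. Illustration.** The documents give neither a slope nor an expected Rail pre-operative mean, so both are assumptions here. The slopes run from 0.23 (near the floor) to 0.30 (the highest floor among rows with n ≥ 31). The literature pre-operative mean is 15560.7/639 = 24.35, rounded to 24.4. There is no device effect at equal pre-operative kyphosis, and n = 173. Shift = slope × cohort difference; SE = 8.4/√173 = 0.639; rejection comes from the noncentral t with parameter shift/SE.

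| Slope | Cohort difference | Shift | Rejects, SD 8.4 | Rejects, SD 12.2 |
|---|---|---|---|---|
| 0.23 | 2 | 0.46 | 11% | 7.8% |
| 0.23 | 3 | 0.69 | 19% | 11.5% |
| 0.30 | 2 | 0.60 | 15% | 9.9% |
| 0.30 | 3 | 0.90 | 29% | 16.2% |

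SD 12.2 is the largest SD of difference in the table. Nearly all the excess lies on one side, set by the direction of the imbalance. In the opposing direction, power for a true 1.8-degree difference at SD 8.4 falls from 80% to 55% / 41% (slope 0.23) or 46% / 29% (slope 0.30).

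**7. How far do whole series lie from 24.35?** The three papers (n = 146, 83, 410) have pre-operative means of 26.40, 23.00 and 23.90, that is +2.05, −1.35 and −0.46 after unrounded subtraction. One of three reaches 2 degrees and none reaches 3.

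**8. Would regression centred at 24.4 be safer?** Suppose instead that the literature measured kyphosis with a constant offset d from the central laboratory. Pre-operative and follow-up readings move together, so raw change is unaffected. The intercept at 24.4 is biased by slope × d. With pre-operative SD 13.4 (pooled over the table rows), s_res = √(8.4² − (slope × 13.4)²) = 7.81 or 7.38, and SE = s_res × √(1/173 + d²/(172 × 13.4²)) = 0.60 to 0.61 (slope 0.23) or 0.57 to 0.58 (slope 0.30). At d = 2 / 3 the regression rejects in 12% / 20% (slope 0.23) to 18% / 34% (slope 0.30), while the raw test stays at 5%.

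**The case against.** **The t-test is valid for what it tests.** The formal hypotheses concern the raw mean, and at a raw mean of 2.2 the 12.3 test rejects in 5% of trials. This stands. A reader might infer that the plan's type I error is 11% to 29%; the documents do not support that. The percentages refer to a different null, no device effect at equal pre-operative kyphosis, and measure comparability.

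**The imbalance may be small and the slope weak.** This also stands in part. By whole series, 2 degrees is seen once in three and 3 degrees not at all. The paper with the highest pre-operative mean has the smallest mean loss (0.87, against 2.80 and 2.35), the reverse of the predicted order, so other differences between series are present. A reader might take the 0.54 slope at face value, which gives 39% / 71% at SD 8.4. That would need pre-operative kyphosis to explain (0.54 × 13.4)²/8.4², about 74%, of the variance in change, and it should not be relied on.

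**Adjustment could introduce error.** Step 8 bears this out. Section 12.2 does not say how the literature angles were measured, while Section 12.8 uses a central laboratory. So the regression should not replace the primary test.

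**Baseline will be summarised anyway.** True, and an imbalance would be visible, but the plan does not say what would follow from it.

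**Rod material.** A reader might infer that the series were not CoCr. The documents do not show that either: the listed titles neither name CoCr nor exclude it.

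**Conclusion.** The concern holds as a weakness of the benchmark, with a secondary gap on case mix.

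The firm parts need no modelling assumption. The benchmark is not documented as CoCr. The OPC of 2.2 does not follow from the table (2.07, or 1.60 depending on one inconsistent row). The sign treated as favourable in 12.3 contradicts the success definition in 12.2. The hypothesis takes three incompatible forms. The 2.07 gap is minor on its own; the n = 299 row is not.

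The case-mix part is conditional. The absence of any check is a fact of the plan, but its effect depends on an assumed slope of 0.23 to 0.30, an assumed true cohort difference of 2 to 3 degrees, the chosen SD and the 12.3 reading of the test. Even in the worst case tabulated, most trials would not reject. This should be corrected before the 24-month data are analysed. Confidence is medium.

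**What to change.** 1. **Reconcile Sections 12.2, 12.3 and 12.5.** State the sign of correction and which direction favours Rail, one hypothesis, one threshold and one test. Resolve the n = 299 row and recompute the OPC from the table rows. This needs a protocol amendment, not only new analysis wording.
2. **Document the comparator in 12.2.** State for each row whether it meets Section 4.3, and recompute the OPC from the rows that do. If rod material cannot be established, limit the conclusion to published posterior instrumentation rather than CoCr.
3. **Keep the reconciled unadjusted test as primary and add to 12.5 a prespecified sensitivity analysis.** Regress 24-month change on pre-operative thoracic kyphosis, centred at the n-weighted pre-operative mean of the OPC rows (24.4 for the current table), and compare the intercept with the same threshold. Report the Rail pre-operative mean and SD beside the table's. If the two analyses disagree, describe the primary conclusion as not robust to case mix.

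**Cost.** One extra regression on data already collected, a return to the three cited papers, and possibly a narrower comparator claim.

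**Limits.** The adjustment covers pre-operative kyphosis only and assumes that the within-cohort line applies at 24.4. It is vulnerable to a measurement offset between the literature and the central laboratory. Other differences from the literature series remain.

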12.4 Analysis Populations

Analysis Populations are defined as follows:

- The Intent-to-Treat (ITT) population includes all enrolled subjects.
- The Per-Protocol population includes all enrolled subjects who have no major protocol violations (defined as not meeting inclusion/exclusion criteria or not being consented properly).

The effectiveness analysis will be performed on the ITT population. Analysis of the per-protocol population will be confirmatory of the ITT analysis. The safety analysis will be performed on the ITT population.

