8 STUDY ENROLLMENT/EVALUATIONS

8.1 Patient Screening and Enrollment

Consecutive patients who potentially meet the study inclusion and exclusion criteria will be screened for eligibility. Diagnostic imaging studies to confirm the diagnosis of AIS with a Lenke type 1 or type 2 curve must be completed within 90 days of the planned date of surgery. If, at an interim point following the initial imaging, and prior to surgery, the subject experiences a significant change in his/her clinical presentation, the changes should be documented and the images repeated. Patients will be screened as follows:

- Consecutive patients are potentially eligible for entry into the study based on their age and whether their medical condition appears to generally fit the characteristics specific to this study.
- After the study is explained and questions are answered to the satisfaction of the prospective study participant, the patient being invited to participate in the study indicates their consent by signing the consent form (or a separate assent form, if required by your IRB/EC.) Any patient under the age of 18 being invited to participate in the study indicates their verbal assent, and their parent/guardian signs the consent form.
- *If required by your institution and/or IRB/EC:* If the child reaches the age of majority during the course of the study, consent to continue (re-consent) must be obtained using the current, approved consent form prior to any further study-specific procedures or assessments.
- A patient is considered enrolled in the study after signing the IRB/EC approved informed consent. Consented patients complete the remainder of the screening process to confirm study eligibility. Patients who do not fulfill the screening criteria are considered Screening Failures and will be documented on the Screening & Enrollment Log. Screening failures will not count against the total number of subjects eligible for analysis.
- Subjects who have signed (or had a parent/guardian sign) the informed consent and fulfilled the Inclusion/Exclusion criteria are then scheduled for surgery. It is important that surgery be scheduled within 90 days from the dates of the required pre-operative x-rays and within 90 days from the date that the subject completed the required pre-operative questionnaires for the study.

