8.3 Hospitalization/Surgery/Discharge

Subjects will be admitted to the hospital according to the Investigator's standard for non-cervical spine surgery. Prophylactic antibiotics may be administered prior to surgery in accordance with the surgeon's standard of care and anesthesia will be administered per standard operating procedures. The system will be implanted in accordance with methods detailed in the instructions for use for the MESA Rail Deformity System.

Data points required on the Operative case report form must be documented at the time of surgery. Intra-operative adverse events must be recorded and documented on an Adverse Event case report form.

A Subject may be excluded from the study intra-operatively at the discretion of the Investigator if unexpected findings/occurrences dictate deviation from the intended study procedure. Justification for an intra-operative exclusion and alternative surgical procedure must be fully documented in the subject's medical record and on the Study Exit case report form. A subject who is excluded intra-operatively will be considered an overall treatment failure.

If the patient experienced an adverse event(s) during the hospitalization it should be documented and recorded on an Adverse Event case report form. The subject may be instructed to return to normal activity at the discretion of the Investigator.

Additional post-operative restrictions may be imposed according to the standard of care normally utilized by the Investigator. In addition, subjects should be instructed to notify the Investigator if experiencing untoward events including but not limited to noticeable pain, numbness, tingling, or weakness that does not decrease with rest, swelling of the lower extremities that does not decrease, or increased pain, erythema, edema or drainage from the surgical incision. The Investigator should then determine if an evaluation is warranted.

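### The Per-Protocol set in Section 12.4 is defined by eligibility and consent alone, so it cannot test whether the ITT result depends on receiving the Rail or on in-window films

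*Combined protocol and SAP*

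**What the plan says.** Section 12.4 defines two populations. For the first, "The Intent-to-Treat (ITT) population includes all enrolled subjects". The second is the enrolled subjects who have "no major protocol violations (defined as not meeting inclusion/exclusion criteria or not being consented properly"). Effectiveness is analysed on ITT, and "Analysis of the per-protocol population will be confirmatory of the ITT analysis".

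Four other places decide who falls into these sets:

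- **Enrolment and screening (Section 8.1).** "A patient is considered enrolled in the study after signing the IRB/EC approved informed consent", which is before eligibility has been fully checked. The same section adds that "Screening failures will not count against the total number of subjects eligible for analysis".
- **Intra-operative exclusion (Section 8.3).** "A Subject may be excluded from the study intra-operatively at the discretion of the Investigator". "Justification for an intra-operative exclusion and alternative surgical procedure must be fully documented", a Study Exit form is completed, and the subject is to be regarded as a treatment failure overall.
- **Baseline imaging (Section 8.1).** Diagnostic imaging "must be completed within 90 days of the planned date of surgery", and surgery is to be scheduled within 90 days of the pre-operative films. Neither rule is among the criteria in Section 7.2.
- **24-month visit (Section 8.6.1).** The window is ±2 months. It too is outside Section 7.2.

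**The concern.** A per-protocol analysis is useful beside ITT because it removes subjects whose treatment or measurement departed from the plan and shows whether the answer changes. Here the exclusions concern who should have entered the study, not what happened to them afterwards. The definition ignores the two departures that bear most directly on a 24-month change in thoracic kyphosis: not having the Rail, and having one of the two films taken at the wrong time.

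This matters more because Section 12 names no other sensitivity analysis of the primary endpoint. The roll-in comparison in Section 3 concerns surgeon experience. Section 12.2 also states the primary hypothesis as non-inferiority in one place and superiority in another. Under non-inferiority, a check on subjects actually treated is normally expected. If ITT and Per-Protocol agree, the report could present that as support on adherence and timing, which the set was never built to examine.

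**Working it through.** **Step 1. Apply the definition to each type of subject.** The only tests in Section 12.4 are the Section 7.2 criteria and proper consent.

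| Subject (eligible and properly consented unless stated) | In ITT? | In Per-Protocol? |
|---|---|---|
| Consents, qualifies, never has surgery | Yes | Yes |
| Excluded in theatre, alternative procedure (8.3) | Yes | Yes |
| Pre-operative films more than 90 days before surgery (8.1) | Yes | Yes |
| 24-month films outside ±2 months (8.6.1) | Yes | Yes |
| Found ineligible after surgery | Yes | No |
| Improper consent discovered later (reporting duty in 14.2) | Yes | No |
| Screening failure | Unclear: 12.4 read with the enrolment rule in 8.1 says yes; the screening-failure sentence in 8.1 points to no | No |

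The sets differ only in the last three rows. The first four rows are the departures from treatment or timing, and both sets treat them identically.

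**Step 2. Reproduce the plan's sample size.** Inputs from Section 12.3: Rail mean 4.0, benchmark 2.2, SD 8.4, two-sided one-sample t-test at 0.05, 80% power, about 15% attrition.

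- Difference = 4.0 − 2.2 = 1.8.
- The noncentral t calculation gives n = 173, with power 0.8003.
- Enrolled = 173 / (1 − 0.15) = 203.5, rounded up to 204.

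Both figures reproduce, and the point disputes neither.

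**Step 3. Illustrate what the definition leaves in.** The documents give no non-implantation rate, so the following is assumed: a fraction f of 173 analysed subjects did not receive the Rail, and each contributes a value averaging c, with c = 2.2 (the benchmark) or c = 0. The analysed mean is (1 − f) × 4.0 + f × c. Power is for the Section 12.3 test against 2.2 with SD 8.4.

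| f | Mean (c = 2.2 / c = 0) | Power, n = 173 (c = 2.2 / c = 0) | Implanted only: n, power |
|---|---|---|---|
| 1% | 3.982 / 3.960 | 79.2% / 78.2% | 171, 79.6% |
| 2% | 3.964 / 3.920 | 78.4% / 76.4% | 170, 79.3% |
| 5% | 3.910 / 3.800 | 75.9% / 70.2% | 164, 77.9% |
| 10% | 3.820 / 3.600 | 71.3% / 58.7% | 156, 75.8% |

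Example: f = 5%, c = 0 gives 0.95 × 4.0 + 0.05 × 0 = 3.8, a difference of 1.6 from 2.2. The Per-Protocol set as now defined carries the same dilution as ITT; a set restricted to implanted subjects does not. These are conditional figures, not estimates, and they apply only if such subjects supply a value.

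**Step 4. Ask whether they supply one.** A subject never operated on has no post-operative film. One excluded in theatre completes a Study Exit form and may have no 24-month film. Section 12.5 compares a mean correction with 2.2 degrees and gives no rule for turning a treatment failure into a number. The effect of these subjects on either analysis is therefore undefined.

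**The case against.** The strongest reply is that ITT is primary, so a narrow Per-Protocol set can do little harm, and that subjects without the Rail may have no endpoint and drop out of both means. The first part stands: the primary test and the sample size are untouched. The second part may be right in practice, but the plan does not say so, and it does not apply to subjects with out-of-window films, who do contribute values.

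A second reply is that the documents limit the problem elsewhere. Section 4.2 describes the treatment group as patients treated with the Rail. Some Section 7.2 criteria, such as the minimum number of instrumented vertebrae and age at surgery, can be breached as late as the operation. Section 8.1 requires repeat imaging after a significant clinical change. A postponed operation acquires a new planned date, so a stale baseline need not comply with the 90-day rule. These narrow the gap. They do not close it, because Section 12.4 refers only to eligibility and consent, and breaching the 90-day rule is not a major violation on any reading.

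A reader might go further and infer that the Per-Protocol set removes only people whom screening has already removed. The documents do not support that. Section 14.2 expects consent failures to be found and reported, ineligibility can surface after surgery, and the status of screening failures in ITT is itself unsettled.

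Nor does high expected agreement between the two analyses measure the defect. Any per-protocol set that overlaps heavily with ITT will usually agree with it, including the one proposed here.

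Finally, requiring a 24-month film in window selects on attendance after treatment. That is a real cost, acceptable in a supporting analysis but not in the primary one.

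**Conclusion.** The concern holds as a fault in a stated rule. Section 12.4 draws the Per-Protocol set by eligibility and consent only, so it retains subjects without the Rail and subjects with out-of-window films, and it cannot test sensitivity to either departure despite its confirmatory role. This follows from the text and needs no assumed rate.

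The size is unknown. The Step 3 illustration runs from under 2 points of power lost at 1% non-implanted (80.0% to 79.2% or 78.2%) to about 21 points at 10% with c = 0 (80.0% to 58.7%). It rests entirely on assumed rates and on those subjects contributing values.

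It would be tempting to conclude that the Per-Protocol analysis confirms almost nothing. The documents do not support that: it still checks late-found ineligibility and improper consent, and how much that adds depends on rates they do not give. The point does not undermine the ITT analysis or the 173/204 sample size. It should be corrected before outcomes are known, because a Per-Protocol definition revised afterwards carries little weight.

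**What to change.** Redefine the Per-Protocol set in Section 12.4 as eligible, properly consented subjects:

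1. who had the MESA Rail implanted and were not excluded intra-operatively;
2. whose pre-operative AP and lateral films were taken within 90 days before the actual surgery date;
3. whose 24-month films fall within the ±2 months already stated in Section 8.6.1.

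The actual-date check in item 2 is for this definition only and leaves clinical scheduling in Sections 8.1 and 8.2 as it is. Reconcile Section 8.1 (enrolled at consent; screening failures not counted) with Section 12.4 (ITT is everyone enrolled), so that it is clear whether screening failures are in ITT. State in Section 12.5 how a treatment failure under Section 8.3 enters the mean, or that it does not.

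The cost is mainly wording. Surgery date and system details are listed in Section 8.3.1, and the films are scheduled in Section 8.6.1. Film dates are not listed as a data item, so the sponsor should confirm that they are captured. The set will be somewhat smaller. If 156 of 173 remained (the 10% row in the working), the standard error would rise from 8.4/√173 = 0.639 to 8.4/√156 = 0.673, about 5%. Selection on 24-month attendance should be acknowledged when the result is reported. ITT stays primary, and 173 and 204 stand.
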